5.6.5. Procedural Pain

Participant assessment of procedural pain (pain during injection) on an 11-point scale ranging from 0 (no pain) to 10 (worst pain imaginable) after each treatment will be summarized. The summary will be performed by treatment group for TP and MP as described in [Table 5-11](#).

Table 5-11 **Procedural Pain Analyses**

Endpoint	Description	Timing	Methodology
Procedural pain	Summary of pain scores as continuous scale	Initial, Touch-up, Maintenance	Continuous descriptive statistics

5.6.6. Other Safety Endpoints

Other safety endpoints include the line change on Snellen visual acuity, confrontational visual fields, ocular motility, EI assessment of facial sensation, pronunciation video recording, the global score of jaw functional limitation (see Section 6.5.3), and concomitant medications and concurrent procedures.

The other safety endpoints will be summarized by treatment groups, for VT and VMT where applicable, respectively, except for concomitant medications and concurrent procedures, where listings will be provided for the Safety Population.

Line change based on Snellen visual acuity using the formula below, confrontation visual fields, and ocular motility assessments evaluated by the TI (or designee) will be summarized by descriptive statistics. Baseline in the below formula is the pre-treatment value prior to the most recent treatment.

Line change = $10 \times [\log_{10} (d_{\text{baseline}}/20) - \log_{10} (d_{\text{follow-up}}/20)]$
where d_{baseline} = denominator of the Snellen equivalent unit at baseline,
 $d_{\text{follow-up}}$ = denominator of the Snellen equivalent unit at follow-up visit

Facial sensation is based on the 2-point discrimination test and a light touch test. The 2-point discrimination is tested at 4 locations (anterior to the jowl and posterior to the jowl on each side of the jawline), and the number and percent of participants who are able to feel the 2 points will be summarized by distance, location, and treatment group. The light touch is tested at the same 4 locations as the discrimination test, and the smallest filament size that the participant felt the stimulus will also be summarized by location and treatment group.

Safety findings from the pronunciation video recordings will be summarized for actual and change from baseline values by visit and by treatment group, for VT and VMT where applicable, respectively. Values of “No Data/Inaudible Response” will be considered as missing data, and no imputation will be done.

The WHO Drug Dictionary Enhanced 201703 or newer will be used to classify prior and concomitant medications by therapeutic class and drug name. Prior medication is defined as any medication taken before the start date of the study treatment for treatment group, or before the randomization date for control group. Concomitant medication is defined as any medication

taken on or after the start date of study treatment for treatment group or on or after the randomization date for control group.

Actual and change from baseline values for overall (including all items) and the 3 subscales of mastication, mobility, and verbal and non-verbal communication from the Jaw Functional Limitation Scale will be summarized using descriptive statistics by treatment group for the VT and VMT populations. The overall score will be computed as the mean of the available items. Details on the algorithm can be found in Section 6.5.3. Baseline for the control group during TP is defined as the last non-missing value prior to receiving optional treatment.

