- Tenderness or pain in the jaw when chewing, which can usually be treated with over-the-counter painkiller and generally resolves within a few days
- Numbness, problems with chewing and mild speech related difficulties which typically resolve without treatment within a few days
- Rare cases of allergy, severe sensitivity, localized inflammation and abscesses
- Very occasionally, delayed side effects can occur many months after the treatment. These delayed side effects may include: lumps, bumps, nodules, cysts, swelling, pain, bruising, skin tightness, and product dislocation.
- In rare circumstances, facial fillers have been injected into blood vessels causing blockage and embolization which can result in skin necrosis, ulceration, or vision changes. Risks to vision include complete blindness, partial blindness, blurred vision, double vision, loss of peripheral vision, loss of a portion of the visual field or anterior segment ischemia (characterized by decreased vision and pain). These effects can be temporary or permanent but are rare.
- In rare circumstances, facial fillers have been associated with granulomas, which are small inflammatory nodules under the skin.
- In rare circumstances, stroke

Unforeseeable risks or results are also a possibility. The risk of developing a serious complication is small. If a complication occurs, subjects will be advised to contact the TI who will use his/her medical judgment to do whatever is necessary to treat the subject. In the event of vision loss, the subject must also be referred to a retinal specialist for evaluation and appropriate care.

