- ! For applicable effectiveness and safety endpoints, baseline is defined as the last non-missing value on or before the latter of randomization date or first treatment date in the control period, unless otherwise specified.
- ! Descriptive statistics for continuous variables include the sample size (N), number of non-missing observations (n), mean, standard deviation, median, 1st and 3rd quartiles, minimum, and maximum. For continuous data, a 2-sample t-test or Wilcoxon rank test will be used for between group comparisons as appropriate, unless stated otherwise. Specified that 95% CI for continuous variables will be based on the standard normal distribution in Section 5.1.
- ! Summary statistics for categorical variables include the sample size (N1), frequency count, and percentage. Ordinal categorical variables will be analyzed using the Cochran-Mantel-Haenszel test. Nominal variables will be analyzed using Pearson's chi-squared test or Fisher's exact test as appropriate. The 95% CI will be computed using the exact binomial method.
- ! The level of significance used for all statistical tests will be 0.05, 2-sided, unless stated otherwise.
- ! The change from baseline values will be computed as the value for the post baseline visit minus the baseline value, unless otherwise indicated.
- ! In the event if any data collected was after exit, it will not be included in tables but will only be presented in the listings.
- ! All statistical analysis will be performed using SAS version 9.3 or higher.
- ! MedDRA 22.1 or newer will be used to code AEs and medical history.
- ! WHO Drug Dictionary 201703 or newer will be used to code medications.

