6.4.1.2. Safety

No analysis windows are required for TEAEs, ISRs, Snellen visual acuity, confrontational visual field, and ocular motility assessments. Nominal visits will be used for summarizing Snellen visual acuity, confrontational visual field, and ocular motility assessments. Pronunciation videos

and facial sensation assessments will be summarized using analysis visit windows in [Table 6-3](#) and [Table 6-6](#) for the treatment group during the TP and MP, respectively, and in [Table 6-4](#) and [Table 6-5](#) for the control group during the CP and TP, respectively. Additionally, Jaw Functional Limitation Scale will be summarized using the analysis visit windows in [Table 6-7](#) for the treatment group during the TP and MP and in [Table 6-8](#) for the control group during the TP.

Table 6-7 Jaw Functional Limitation Scale Visit Windows for Treatment Group during the Treated and Maintenance Periods

Scheduled Visit for Safety Measure	Target Day of the Visit	Analysis Visit Window with Touch-up
Screening ^a	N/A	Screening visit; No more than 30 days prior to randomization
Baseline	N/A	Randomization/Initial Treatment visit
Day 14 After Initial Treatment	Day 15 Post Randomization/Initial Treatment	Day 2 to Day 23 of Randomization/Initial Treatment Period
Touch-up Treatment ^b	Day of Touch-up Treatment	Day 24 of Randomization/Initial Treatment Period to Touch-up Treatment Date
Day 14 After Touch-up Treatment	Day 15 Post Touch-up Treatment	Day 2 to Day 23 of Touch-up Treatment Period
Last Treatment ^c	Day of Last Treatment	Day of Last Treatment (Initial or Touch-up)
Month 1	Day 31 Post Last Treatment	Day 24 to Day 61
Month 3	Day 91 Post Last Treatment	Day 62 to Day 136
Month 6	Day 181 Post Last Treatment	Day 137 to Day 226
Month 9	Day 271 Post Last Treatment	Day 227 to Day 316
Month 12	Day 361 Post Last Treatment	Day 317 to Maintenance Treatment Date ^d or Study Exit Date, whichever is earlier
Maintenance Treatment ^d	Day 1 Maintenance Treatment	Day of Maintenance Treatment
Day 14 Maintenance Treatment	Day 15 Post Maintenance Treatment	Day 2 to Day 23 Post Maintenance Treatment
Month 1 after Maintenance Treatment	Day 31 Post Maintenance Treatment	Day 24 to Day 61 Post Maintenance Treatment
Month 3 after Maintenance Treatment	Day 91 Post Maintenance Treatment	≥ Day 62 Post Maintenance Treatment

^a Participants may have screening and randomization on the same day. In such cases, only randomization visit is relevant.

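### Facial sensation is summarized only visit by visit, so the planned tables bound, but do not count, the participants with new sensory loss

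*SAP*

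**What the plan says.** SAP 5.6.6 plans two summaries of facial sensation. Two-point discrimination is the number and percent of participants "able to feel the 2 points will be summarized by distance, location, and treatment group". For light touch, "the smallest filament size that the participant felt the stimulus will also be summarized by location and treatment group". SAP 6.4.1.2 adds that "facial sensation assessments will be summarized using analysis visit windows in" Tables 6-3 to 6-6, which makes these per-visit results. Protocol 8.3.4 asks only for a descriptive summary. Neither document names a change from baseline, a shift table or a count of participants who worsened for this measure.

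Three neighbouring measures in SAP 5.6.6 are treated differently:

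- Pronunciation: "Safety findings from the pronunciation video recordings will be summarized for actual and change from baseline values by visit and by treatment group".
- Jaw Functional Limitation Scale: "Actual and change from baseline values for overall (including all items) and the 3 subscales" are summarized.
- Snellen acuity: a line change is computed for each participant, and "Baseline in the below formula is the pre-treatment value prior to the most recent treatment".

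Confrontational visual fields and ocular motility, like facial sensation, get descriptive statistics with no stated change.

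SAP 5.1 gives the general arithmetic: "The change from baseline values will be computed as the value for the post baseline visit minus the baseline value, unless otherwise indicated". It does not say which endpoints receive a change summary.

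**The concern.** The safety question for this test is whether a participant who had sensation before injection lost it afterwards. Protocol 11.1.1 lists "Numbness, problems with chewing and mild speech related difficulties" among the known potential adverse events, and Protocol 7.2 names the evaluator's sensation test as a safety measure in its own right.

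The paired data exist. Protocol Tables 2, 3 and 5 schedule the test before initial, touch-up and delayed treatment, at the maintenance visit, and at the follow-up visits from Month 1. Table 4 schedules it for untreated controls at randomization and Months 1, 3 and 6.

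A per-visit percentage does not use the pairing. If some participants lose the response while others gain it, for example through familiarity with the test, the percentage can stay level. Dropout adds to this, because the people behind the percentage at one visit need not be those behind it at another.

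**Working it through.** **Plan's own figure.** The documents give no figure for facial sensation. The only number borrowed here is the 176 treated participants in SAP Section 3. It follows from the stated minimum sizes and dropout rates: 144 × 0.95 = 136.8 and 48 × 0.85 = 40.8. Rounding each down gives 136 + 40 = 176.

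**Assumptions.** The percentages able to feel two points are assumed, over a wide range. The same 176 people are taken to be tested at both visits. The planned table is split by treatment group, so each column holds fewer people. The bounds as percentages do not depend on N, apart from rounding.

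**Formula.** At one location and distance, let *b* be the number who felt two points at baseline but not at follow-up (new loss), and *c* the reverse (gain). Let F0 and F1 be the numbers able to feel two points at baseline and at follow-up.

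- F0 − F1 = *b* − *c*, so the planned table gives the net difference and not *b*.
- The limits on new loss are max(0, F0 − F1) ≤ *b* ≤ min(F0, N − F1).

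**Results for N = 176:**

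| Assumed % able, baseline → follow-up | F0 → F1 | N − F1 | Possible new losses | Upper limit, % |
|---|---|---|---|---|
| 98 → 98 | 172 → 172 | 4 | 0 to 4 | 2.3 |
| 95 → 95 | 167 → 167 | 9 | 0 to 9 | 5.1 |
| 90 → 90 | 158 → 158 | 18 | 0 to 18 | 10.2 |
| 80 → 80 | 141 → 141 | 35 | 0 to 35 | 19.9 |
| 50 → 50 | 88 → 88 | 88 | 0 to 88 | 50.0 |
| 90 → 88 | 158 → 155 | 21 | 3 to 21 | 11.9 |

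**Reading the table.** If nobody gains (*c* = 0), then *b* = F0 − F1 and the planned table shows every loss. In the last row that is 158 − 155 = 3. Each gain hides one loss. The upper limit is reached only when every participant unable to feel two points at follow-up could feel them at baseline.

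The same logic holds for light touch: the distribution of filament sizes at two visits does not fix how many participants needed a larger filament than before. The number worse at any of the four locations cannot be recovered from location-by-location summaries either.

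**The case against.** The strongest case for the plan has five parts.

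1. **Facial sensation is not singled out.** A reader might infer that it alone lacks a change measure. It does not: visual fields and ocular motility have none either. A count and percentage also follows the SAP 5.1 convention for categorical data. This stands, and the contrast is confined to pronunciation, jaw function and Snellen acuity.
2. **Masking is not shown to happen.** A reader might infer that a real signal will be missed. The documents do not support that. They give no baseline rates and no retest variability, the lower limit is zero in every equal-percentage row above, and loss that is mainly in one direction would lower the percentage. This stands: the point is that the count is left undetermined.
3. **Controls are tested too.** SAP 6.4.1.2 applies the Table 6-4 windows to untreated controls, whose results would help to show any learning effect. This stands in part. Their per-visit percentages are also net figures, and SAP 5.6.6 names the treated and maintenance populations where applicable, so how the two sections fit together is not fully explicit.
4. **Numbness can be captured as an adverse event.** Adverse events are solicited at every visit and safety call, and all treatment-emergent events are listed. This stands for symptoms that participants notice and report. It does not replace a comparison of test results.
5. **Table specifications are in a separate document** (SAP Section 1). A shift table may be there. The SAP does not require one.

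**Conclusion.** The point holds as a limited weakness in a safety summary. SAP 5.6.6 collects paired sensation tests and plans to report them unpaired. The consequence depends on how many participants can feel two points: at most 4 of 176 hidden losses at one location and distance if 98% can at both visits, at most 18 at 90%, and at most 35 at 80%. These limits rest on assumed percentages, equal at both visits, and on no dropout. The primary endpoint, the hypotheses and the sample size are unaffected. The change is still worth making, because adverse event reports and control-group percentages do not supply the count of new losses, and the data for it are already scheduled.

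**What to change.** In SAP 5.6.6, add for each location and visit, among participants with both values:

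- two-point discrimination at each distance: felt to not felt, not felt to felt, and unchanged;
- light touch: smallest filament felt larger, the same or smaller than at baseline;
- the number of participants worse at any location.

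State the baseline for each period:

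- treatment group: last value before initial treatment;
- delayed-treatment controls: last value before optional treatment;
- maintenance period: last value before maintenance treatment.

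This has to be written out. The general baseline in SAP 5.1 is tied to the control period, and the pre-optional-treatment baseline in 5.6.6 is stated only for the Jaw Functional Limitation Scale.

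Present the same table for untreated controls in the control period, with baseline at randomization, so that test-retest variation can be judged. This matters most for the any-location count, which pools several tests and will pick up chance shifts.

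The cost is one additional descriptive table. It needs no new data, visits or participants. The downside is that some of the shifts shown will be measurement noise.

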#### 2.2 Risk and Benefit

HA skin injection procedures carry the usual risks of erythema, pain, tenderness, swelling, itching, bleeding, bruising, lumps/bumps, firmness (induration), and skin infection. Allergic reactions to anesthetic agents are rare and may include skin rash, redness, itching, hives, burning, stinging, swelling, tenderness, and transient (temporary) loss of skin color.

Results of a multicenter, single-blind, randomized, controlled clinical study (V25L-001) conducted in 120 subjects demonstrated that VOLUX XC injectable gel was safe and effective in restoring and creating facial volume, and in sculpting, shaping, and contouring in the chin and jaw area. The primary effectiveness measure (glabella, subnasale, and pogonion angle measured by the blinded image-analysis technician from digital images of the subject's facial profile) showed significant improvement in projection of the chin. Procedural pain in this study was minimal. The most common injection site responses (ISRs) after initial/touch-up treatment were firmness, tenderness to touch, and swelling, and most ISRs resolved within 1 week of treatment. Prior to repeat treatment, treatment-related adverse events (AEs) were observed for 38.7% of subjects treated with VYC-25L injectable gel, with the most common being mild injection site mass (verbatim term: lumps/bumps). These are commonly reported events following treatment with HA dermal fillers. Most treatment-related AEs did not require treatment. A small percentage of treated subjects (3.4%, 4/119) after initial or touch-up treatment and 1.1% (1/89) after repeat treatment experienced

treatment-related AEs of speech disorder (investigator term: unclear pronunciation), considered to be related to the physical presence of filler in subjects' chin. The events were mild in severity, self-limiting, and resolved without sequelae within a few days. The subjects who experienced these events tended to have larger than average volumes injected into the pogonion and mentum (> 1.5 mL in each area). No deaths or treatment-related serious adverse events (SAEs) were observed.

The results of Study V25L-001 demonstrate that treatment with VOLUX XC injectable gel is an effective treatment for restoring and creating facial volume. The safety profile indicates that VOLUX XC injectable gel is safe and well tolerated by subjects in all treated areas.

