#### 6.2 Procedures to be Performed

The TIs will be trained in the injection technique, and TIs and EIs will be trained in the use of the ALJDS prior to initiating enrollment.

Throughout the study, to the extent possible, it is recommended that all treatments and safety assessments for a particular subject be performed by the same TI (in the case of the facial sensation assessment, by the same EI), and effectiveness assessments (ALJDS and Global Aesthetic Improvement Scale [GAIS]) be performed by the same EI. If it is not possible to use the same evaluator to follow the subject, it is recommended that evaluations overlap

EIs assessment of facial sensation will be as follows: the EI will test sensation in the chin area using a 2-point discrimination test and a light touch test. Two-point discrimination will be tested at 4 locations (anterior to the jowl and posterior to the jowl on each side of the jawline). Using the \_\_\_\_\_\_\_, the EI will lightly touch the set of prongs to each location on the chin, as specified by the eCRF, while the subject reports whether s/he feels "1" or "2" objects touching his/her skin. The light touch test will be performed at the same 4 locations on the jawline. The EI will press \_\_\_\_\_\_\_ (specified on the eCRF) against the subject's skin and record the smallest filament size that elicits a response at each assessed location.

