#### 9.1.2 Instructions for Use and Administration

For investigational use in this study, VOLUX XC injectable gel with lidocaine will be administered via the supplied needles (27 G 1/2") or cannula (25 G 1 1/2") to the pre- and post-jowl area, chin, marionette lines, and angle of the mandible to restore jawline definition, provide a smooth contour, and achieve an aesthetically pleasing result. When making an entry point for the cannula, only use the introducer needle that is co-packaged with the provided cannula.

The TI must be experienced in the use and administration of HA implants and be practicing in the field of aesthetic medicine, plastic/cosmetic/reconstructive surgery, or dermatology. Before the study begins, the TI will receive training in the administration of VOLUX XC according to the technique specified for this study.

The TI will use aseptic injection technique and inject the treatment slowly using gentle, even pressure on the syringe. The detailed recommended injection technique is provided in the VOLUX XC IDFU included in the Site Study Binder.

Note: In Study V25L-001, a small percentage of treated subjects (3.4%, 4/119) after initial or touch-up treatment and 1.1% (1/89) after repeat treatment experienced treatment-related AEs of speech disorder (investigator term: unclear pronunciation), which were considered to be related to the physical presence of filler in subjects' chin. The events were generally mild in severity, self-limiting, and resolved without sequelae within a few days. The subjects who experienced these events tended to have larger than average volumes injected into the pogonion and mentum (> 1.5 mL in each area).

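### Pronunciation videos: the pooled code *No Data/Inaudible Response* is set to missing, so a response that could not be made out looks the same as an absent recording and can drop out of the tables

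*SAP*

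**What the plan says.** SAP 5.6.6 (Other Safety Endpoints) states: "Safety findings from the pronunciation video recordings will be summarized for actual and change from baseline values by visit and by treatment group". The populations are the VOLUX-treated and maintenance-treated participants. The next sentence takes the code *No Data/Inaudible Response* and says such values "will be considered as missing data, and no imputation will be done".

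The reason for the videos is in the protocol. Section 2.2 reports "treatment-related AEs of speech disorder (investigator term: unclear pronunciation") in the preceding study of the product. Section 9.1.2 gives the frequency: "a small percentage of treated subjects (3.4%, 4/119) after initial or touch-up treatment and 1.1% (1/89) after repeat treatment". Section 11.1.1 includes in its list of known potential events: "Numbness, problems with chewing and mild speech related difficulties which typically resolve without treatment within a few days".

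SAP 5.1 sets the general content of descriptive tables. Continuous variables carry both a sample size and a count of non-missing observations. Categorical variables carry a sample size, a frequency count and a percentage, and no missing count is named.

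**The concern.** A missing-data rule for a safety measure should not absorb an outcome the measure is meant to detect. Here one code covers a file that was never made and speech that could not be followed. If any of the second kind is real impairment, setting it to missing moves the tables in the favourable direction. The reader of the report could not see that this had happened.

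The SAP is more cautious with other safety gaps. In 5.6.3, a treatment-emergent adverse event with missing severity is summarised at maximum severity, and one with missing relationship is counted as related. The video code gets neither a conservative rule nor a visible count.

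**Working it through.** The plan states no figure for this endpoint, so the check is mainly a reading of the rule against the table conventions.

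**1. What the rule does to three participants, all with a rated baseline**

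| Follow-up | Actual value | Change from baseline |
|---|---|---|
| Rated, worse | shown | shown |
| Recorded, not made out | missing | missing |
| Not recorded | missing | missing |

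SAP 5.1 defines change as the post-baseline value minus baseline, so it is missing whenever the follow-up is missing. The second and third rows give identical output.

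**2. Whether the tables would reveal the loss.** If the rating is handled as continuous, SAP 5.1 gives a non-missing n, so the total missing can be counted but not its cause. If it is handled as categorical, even that total is not guaranteed. SAP 5.6.6 does not say which applies and promises no listing of video results. The table specifications are in a separate document that was not available.

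**3. How far one participant moves a percentage.** Let n participants have a recording at a visit, m of them inaudible, and k of the rest rated worse. The planned table shows k/(n − m). If every inaudible response were true worsening, the figure would be (k + m)/n. The gap is

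(k + m)/n − k/(n − m) = (m/n) × [1 − k/(n − m)], which is at most m/n.

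For n, take the planned minimum treated numbers in SAP 3: 144 × 0.95 = 136.8 and 48 × 0.85 = 40.8. Rounded down, these are 136 and 40, which add to the stated 176. Assuming all have a recording, each inaudible response can shift the percentage by at most:
- randomised treatment group: 1/136 = 0.7 percentage points
- treated controls: 1/40 = 2.5 percentage points

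If m = 0 there is no effect. The documents give no value for m.

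**4. Whether the earlier study's rate can supply m.** The rates are 4/119 = 3.4% and 1/89 = 1.1%. They are adverse event rates, not video ratings. Protocol 2.2 describes those events as mild and over within days. In Protocol Tables 2, 3 and 5 the first video after a treatment falls at Day 30 (before any touch-up) or Month 1; none is scheduled at Day 3 or Day 14. Most events of that kind would have ended before the camera was on. The rate therefore cannot be turned into an expected number of abnormal or inaudible videos.

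**The case against.** The strongest reply is that leaving a descriptive safety rating unimputed is ordinary practice, and that affected participants can appear elsewhere. Speech difficulty reported as an adverse event goes into the tables of SAP 5.6.3, which this rule does not touch. The Jaw Functional Limitation Scale has a communication subscale and is collected at Day 14, before any post-treatment video. Both points stand, and they confine the loss to the video tables. They do not remove it: those other routes rely on the Treating Investigator and the participant, neither of whom is blinded (Protocol 4.3.3), and a measure collected repeatedly should be reported in full.

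Three stronger readings are tempting, and the documents do not support them.

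- **Inaudible is the worst grade.** The rating scale is not in the documents, and the pooled code may reflect sound quality. Impaired speech is a possibility, not a finding.
- **The known 3.4% speech-disorder rate would be under-reported.** That is an adverse event rate, reported in tables the rule leaves alone, and the video timing argues against carrying it over.
- **Participants numb to light touch are also removed.** Protocol 6.2 has the evaluator "record the smallest filament size that elicits a response at each assessed location", and SAP 5.6.6 says "the smallest filament size that the participant felt the stimulus will also be summarized by location and treatment group". Neither states how a lack of response to any filament is handled, but no rule discards it. The instrument text is blanked out and the detail is left to the eCRF, which may hold such a code. Two-point discrimination at the same 4 locations also keeps failures visible, because "the number and percent of participants who are able to feel the 2 points will be summarized by distance, location, and treatment group".

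**Conclusion.** The point holds for the pronunciation videos. The SAP states a rule that treats an inaudible response as missing and pools it with an absent recording, so such participants can leave both the actual and the change-from-baseline summaries without being identified. Any resulting bias would favour the product.

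It is a minor reporting gap. The number affected is unknown and may be 0. The bound of 0.7 percentage points per participant in the treatment group (2.5 in treated controls) assumes the planned minimum numbers, a recording for everyone, and a table read as the proportion worse. No test, significance level, sample size or success criterion depends on it.

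For light touch, nothing more is warranted than asking the sponsor to confirm how no response to any filament is coded on the eCRF.

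**What to change.** In SAP 5.6.6 and the matching table specifications:

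1. Keep the main pronunciation summary as planned, without imputation.
2. Show *No Data/Inaudible Response* as its own row (n, %) by visit and treatment group.
3. Where a recording exists, split that row into inaudible and no data.
4. Add a supplementary row, labelled as possible worsening, counting participants with an audible baseline and an inaudible follow-up.
5. Confirm the eCRF coding for no response to any light-touch filament.

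The cost is a few lines of SAP text and two or three table rows. Step 3 also needs a check that a recording exists for each pooled value. The downside is that technical faults may inflate the supplementary row, so it should be labelled accordingly and kept apart from the main summary.
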